Results. Of 268 patients with PD assessed at baseline, 108 (40.3%) had PD-MCI. After a period of 3.8 ± 0.8 years, 182 (61.2%) patients were re-assessed and 164 analysed (17 excluded due to deep brain stimulation, one patients without classification of cognitive group). At follow-up, 93 (56.7%) patients fulfilled criteria for normal cognitive function (PD-CN), 54 for PD-MCI (32.9%), and 17 (10.4%) had developed dementia. Predictive ratio of baseline cognitive IADL impairment (n=37; 21.3%) for dementia conversion was descriptively higher than for PD-MCI, but highest in patients with both markers [HR=12.01, 95%-confidence interval (CI): 4.47-32.23]. Nearly half of patients (n=10, 47.6%) with baseline classification of cognitive IADL impairment and PD-MCI converted to dementia. Baseline status of cognitive IADL impairment was associated with higher non-motor burden, worse cognitive performance, and more severe IADL progression over the study period. In a post-hoc Receiver Operating Characteristic (ROC) analysis, the FAQ quotient (cut-off >1.008) was confirmed to best predict conversion to dementia compared to other IADL scores. Only two patients with baseline status of cognitive IADL impairment in our sample scored below the newly identified FAQ quotient cut-off of 1.008 resulting in a total of 35 (21.3%) patients with values above this defined cut-off. The FAQ motor score [AUC(area under the curve)=0.60, 95%-CI: 0.52-0.67, $p=0.13$], reflecting predominantly motor aspects on IADL function, was not associated with PDD conversion.

4. Objectives of the study

Based on previous analyses in the sample we suggest that monitoring of both cognition and cognitive ADL impairment reflect neurodegeneration associated to PDD development. This study evaluates markers predicting cognitive and ADL long-term outcome in our sample. Additionally, we will investigate whether ratings of patients or informants best predicted decline of cognitive impairment and/or everyday function. Clinical data along with other clinical marker and biomarker status will be investigated.

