6.1. Study population

Between March 30th, 2014 and December 31th, 2017, we recruited a large cohort of 268 PD patients within the frame of the "Amyloid-Beta in cerebrospinal fluid as a risk factor for cognitive dysfunction in Parkinson's Disease" (ABC-PD, ethic protocol 686/2013B01) study. Follow-up visits were conducted between July 2018 and September 2020, all patients of the ABC-PD study were contacted for re-examination.

We propose a second follow-up of the already existing longitudinal cohort described above with a longitudinal assessment including neuropsychological in-depth endophenotyping and CSF biomarker analyses. In total 182 patients will be invited to participate in the second

follow-up assessment. If patients are not able to attend a clinical visit in-house, possibility of assessments at patients' homes shall be offered. Moreover, if patients are not able to give consent for study participation (confirmed by an independent physician), the legal guardian will be contacted to give study consent for participation. Legal guardians are defined as persons with legal care directive or lasting power of attorney. For drop-outs different reasons for drop-out will be coded (e.g. deceased, disabled, disinterested/refuse study participation, unable to reach/unknown address).

Diagnosis of cognitive impairment:

Patients were classified as PD-MCI according to Level-II Movement Disorder Society recommendations if cognitive impairment was present but did not significantly interfere with everyday function [25]. PDD was defined according to Movement Disorder Society Task Force criteria [17] if cognitive impairment was present and severe enough to impair ADL function unrelated to motor or autonomic symptoms and at least one behavioral symptom was present to support diagnosis. Cognitive impairment was defined according to Level-I (impairment of global cognition) for patients with minimal assessments, or Level-II (performance below 1.5 standard deviation of the population mean reported in the test manuals on at least two tests) for patients assessed using a full cognitive battery. Patients not meeting either of the diagnostic criteria were classified as PD-CN. Cognitive status at follow-up was defined as the primary study outcome.

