Prediction of cognitive progression along with progression in ADL function over time: In patients who completed all visits, the predictive values of baseline/follow-up IADL (patients' self-impression vs. informant-rating), stratification (cognitive IADL impairment vs. motor IADL impairment), cognitive status (PD-CN vs. PD-MCI), and both markers combined (PD-MCI + cognitive IADL impairment) will be calculated using multivariate Cox Proportional-Hazard models. Akaike's information criterion (AIC) and concordance index (C-index) [26] will be used as model fit indices. Logistic regression with follow-up cognitive diagnosis (PD-CN vs. PD-MCI or non-demented vs. PDD) as dependent variable will evaluate whether baseline status of cognitive IADL impairment (FAQ quotient >1.008) predicted risk of PDD conversion independent of other clinical variables (e.g., cognitive status), biomarker profile, and covariates. As a post-hoc exploratory analysis to identify which subscore best predicted PDD conversion, ROC curves will be calculated for all FAQ scores (self- and caregiver-assessment). The optimal score/cut-off will be chosen according to the highest Youden Index. Linear regression will be applied to investigate predictors of neuropsychological scores and IADL measures at follow-up(s).

2. Defining the interaction of progression in markers over time

Generalized linear mixed effects models (GLMMs) will evaluate progression in neuropsychological tests and IADL scores over time. Correlation analyses are planned to investigate association in change of scores over time of different measures.

Sample size calculation:

Between the baseline and first follow-up 17 (10.4%) patients developed PDD within a mean follow-up interval of 3.78 ± 0.84 years (range: 1.67-5.79 years), with higher rates of converters in patients with baseline status of cognitive ADL impairment (29.7%). Estimated follow-up interval between first and second follow-up are expected to be very similar, and a higher rate of patients with cognitive ADL impairment were identified. Moreover, the risk for PDD development is increased in later disease stages [27, 28]. Therefore, a maximum of additional 15 converters are expected.

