Table 2: Overview of clinical assessments conducted at home by study patients

Patient questionnaires (filled out at home):	
Parkinson's Disease Non-Motor Symptoms Questionnaire (PD-NMS-Q)	3 min
Beck Depression Inventory – II (BDI-II)	5 min
Beck Anxiety Inventory (BAI)	2 min
Pfeffer Functional Activities Questionnaire (FAQ)	2 min
Parkinson's Disease Activities of Daily Living Scale	1 min
Parkinson's Disease Questionnaire (PDQ-39)	5 min
Freezing of Gait Questionnaire (FOG)	1 min
Epworth Sleepiness Scale (ESS)	2 min
REM Sleep behavior questionnaire (RBDS-Q)	2 min
Apathy Evaluation Scale (AES)	3 min
Skala zur Allgemeinen Selbstwirksamkeitserwartung (SWE)	5 min
Questionnaire for Impulsive-Compulsive Disorders in Parkinson's Disease-Short (QUIP-Kurz)	3 min
Unified Parkinson's Disease Rating Scale (UPDRS) Parts I-II	6 min
International Consultation on Incontinence Questionnaire-Short Form (ICIQ-SF)	2 min
Patient Perception of Bladder Condition (PPBC)	1 min
Total time of clinical assessment conducted at home by patients:	43 min
Optional: Home-based movement assessment (accelerometry device)	7 days

The Kölner Apraxie Test included for validation of the Dementia Apraxia Test (DATE) as well as the Skala zur Allgemeinen Selbstwirksamkeitserwartung (SWE) will be applied as additional study outcome. All other scales and measurement were also included in the first follow-up of the sample (Title: Cognitive driven ADL impairment as a predictor for PDD; ethic protocol: 284/2018BO1). For this scientific study, all investigations will be performed in an ambulatory setting and need the study participants to be available for at least 3 hours, not including the optional blood marker sampling.

If patients agree to the optional CSF and/or blood collection (see also 8.5):

- Blood collection 15 min
- CSF 30 min
- Bed rest after CSF collection 30 min

Total time for biomarker sampling: 75 min

Invasive biomarker sampling will not be conducted for patients, who are not able to give consent for study participation.

Caregiver assessments:

To validate the patients' self-impression, the following caregiver questionnaires and interview scales will be applied, needing caregivers to be available for at least 38 minutes. Caregiver assessments will only be performed if the respective patient has agreed to the interview.

Table 3: Overview of caregiver assessments

Assessment	Time
Explanation of the study requirements	10 min
Interview-based ratings:	

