11.3. Information and informed consent

Prior to the respective assessments, every prospective participant will be informed in oral and written form about the general goal of the study and how the assessments will be performed. In particular, the informed consent form will contain comprehensive information about contents, objectives, duration, procedures, voluntariness, and possible risks of the study participation. Any kind of questions will be considered and answered. In case of agreement to study participation, the participant has to sign two copies of the informed consent form. One form will be given to the participant and the other form will be stored at the local study centre in a separate folder (not in the medical records).

In addition to the PD patients, caregivers will be contacted and interviewed. Therefore, informed consent will also be obtained from patients' caregivers using a separate caregiver

informed consent form. The patients will be asked to choose the caregiver who will then be contacted for the caregiver assessment.

12. Insurance

A road accident insurance (SV SparkassenVersicherung AG Hessen-Nassau-Thüringen, Wiesbaden) including insurance for accident during study visit will be offered (limited to 145 patients and 90 companions/caregivers).

Insurance Nr.: 50100561414

Date: 01.03.2023 - 31.12.2024

Maximal insurance costs for patient and caregiver:

100.000 EUR disability case

50.000 EUR death

10.000 EUR salvage costs

5.000 EUR cosmetic surgeries

13. Information text and text of the informed consent

See attachments:

- Patient information sheet and informed consent form
- Patient data privacy statement
- Caregiver information sheet and informed consent form
- Caregiver data privacy statement
- Legal guardian information sheet and informed consent form
- Legal guardian data privacy statement
- Questionnaires for informants
- Offer and conditions of road accident insurance (including accident insurance during study visit)

14. Reference list

1. Fereshtehnejad, S.M., et al., *New Clinical Subtypes of Parkinson Disease and Their Longitudinal Progression: A Prospective Cohort Comparison With Other Phenotypes*. JAMA Neurol, 2015. **72**(8): p. 863-73.
2. Fereshtehnejad, S.M., et al., *Clinical criteria for subtyping Parkinson's disease: biomarkers and longitudinal progression*. Brain, 2017. **140**(7): p. 1959-1976.

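### Section 7 compares patient-rated and informant-rated IADL models by AIC without requiring that both models use the same patients

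*Combined protocol and SAP*

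**What the plan says.** Section 4 makes the choice of rater an objective: "we will investigate whether ratings of patients or informants best predicted decline of cognitive impairment and/or everyday function".

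Section 7, under prediction of cognitive progression, begins the Cox analysis with "In patients who completed all visits, the predictive values of baseline/follow-up IADL (patients' self-impression vs. informant-rating", followed by the other predictors. The next sentence names the fit measures: "Akaike's information criterion (AIC) and concordance index (C-index) [26] will be used as model fit indices". The set is fixed by visit completion alone. Nothing requires both ratings to be present, and section 7 has no rule for missing informant data.

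Section 8 (Table 2) lists the patient's FAQ among the questionnaires for all patients. The informant FAQ (Table 3) has an extra condition: "Caregiver assessments will only be performed if the respective patient has agreed to the interview". Section 11.3 adds that the patient names the caregiver and that the caregiver consents separately. The only caregiver number is in section 12, where the accident insurance is "limited to 145 patients and 90 companions/caregivers".

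**The concern.** AIC ranks models only when they are fitted to the same observations. In a Cox model the log partial likelihood is a sum over events, and each term depends on how many patients are at risk. Removing patients and events therefore lowers AIC even when the predictor carries no information. A completer without an informant form would normally be dropped from the informant model by the software and kept in the self-rating model. The informant model could then show the lower AIC because forms are missing and not because it predicts better. The question at stake is the rater comparison in section 4.

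**Working it through.** **Inputs from the documents.** Invited: 182; expected drop-out 20%; planned 145 (sections 6.1 and 6.3). Check: 182 × 0.80 = 145.6, which agrees. Conversions to first follow-up: 17/164 = 10.4%, at 3.78 ± 0.84 years. Further conversions: at most 15 (section 7). So there are 15 events counted from first follow-up, or at most 17 + 15 = 32 from baseline; 32 is an upper bound, since not every early converter need be among the 145. Strongest reported effect: HR 12.01 (4.47 to 32.23) for PD-MCI plus cognitive IADL impairment, carried by 10/0.476 = 21 of 164 patients (section 3.2). It serves here as a benchmark for a very strong marker. The documents give no AIC value and no count of informant ratings to reproduce.

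**Assumed.** Informant coverage. The ratio 90/145 = 62% comes from the insurance limit and is one point in a range, not an estimate.

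**Size effect without any predictor.** The null value is −2 log PL = Σ 2·ln(number at risk), summed over events. The high case has all events before any censoring: Σ 2·ln(n − i), i = 0 to d − 1. In the low case the number at risk falls linearly from n to n/10 across the d events. At 62% coverage, events scale to 32 × 90/145 ≈ 20 and 15 × 90/145 ≈ 9.

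| Patients / events | Low | High |
|---|---|---|
| 145 / 32 | 270.0 | 311.1 |
| 90 / 20 | 149.3 | 175.4 |
| Gap | 121 | 136 |
| 145 / 15 | 126.1 | 147.8 |
| 90 / 9 | 66.6 | 80.2 |
| Gap | 60 | 68 |

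These gaps arise from size alone.

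**Simulation.** 145 patients, 32 or 15 events, one binary rating per rater, visit times normal with mean 3.78 and SD 0.84, informant forms missing at random, 300 runs per scenario (Monte Carlo standard error at most √(0.25/300) ≈ 3 percentage points). The patient model uses all 145; the informant model uses those with a form. Entries are the percentage of runs in which the informant model has the lower AIC (32 events / 15 events).

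| Informant coverage | Patient HR 12, informant no effect | Patient HR 3, informant HR 1.5 |
|---|---|---|
| 62% | 100 / 99 | 100 / 100 |
| 70% | 99 / 96 | not run |
| 80% | 92 / 79 | 100 / 98 |
| 90% | 54 / 45 | 96 / 88 |
| 95% | 16 / 20 | 77 / 73 |
| 98% | 1 / 11 | not run |

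With both ratings uninformative at 62%, the informant model has the lower AIC in 100% of runs (median gap 126 with 32 events, 52 with 15).

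**If every converter has an informant** (62% coverage overall), only the risk sets shrink and the gap is about 2·d·ln(145/90): 2 × 32 × 0.477 = 30.5, or 2 × 15 × 0.477 = 14.3. The informant model then has the lower AIC in 55 / 45% of runs against patient HR 12, and 99.7 / 96% in the moderate contrast.

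**Same patients in both models** (about 90). The informant model has the lower AIC in 48% of runs when both ratings are uninformative, 0 / 4% when only the patient rating works (HR 12), and 100 / 97% when only the informant rating works (HR 12). In the moderate contrast, over coverage of 62 to 95%, it is 11 to 17% (32 events) or 25 to 29% (15 events). The tilt is gone.

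**C-index.** At 62% coverage the informant model has the higher C-index in 45 to 49% of runs under no effect and 0 to 1% against patient HR 12: no size tilt.

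**The case against.** The plan never says that the two models will use different patients. It names one set, "In patients who completed all visits", for all the Cox models, and if both ratings entered one multivariable model the sample would be shared automatically. This stands as a correction of emphasis: the plan is silent and prescribes no error. Silence is still a gap, because separate fits on available cases satisfy the text.

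A reader might infer from section 12 that only 90 of 145 patients will have an informant rating. The documents do not support that. The figure is a limit on an accident policy covering the second follow-up period, whereas the predictors are "baseline/follow-up IADL (patients' self-impression vs. informant-rating", which for conversion by the second follow-up would mainly be ratings already collected. Section 3.1 confirms that both raters were asked earlier, but gives no coverage.

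A reader might also infer that AIC decides the question alone. It does not. The C-index stands beside it, and section 7 adds exploratory ROC curves for self- and caregiver-rated FAQ scores. However, no rule covers disagreement between AIC and C-index, and a C-index from patients with different case mix also calls for a common sample.

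Finally, self-rating coverage was taken as complete, although the patient FAQ is a take-home form. If self-ratings were missing more often, the tilt would run the other way.

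**Conclusion.** The point holds as an omission worth correcting: section 7 does not guarantee that the AICs used in the rater comparison come from the same patients and events. If they do not, AIC favours the rater with fewer of both. The size depends on coverage that the documents do not report. It is decisive at 62%, where the informant model has the lower AIC in nearly all runs. At 90 to 95% it remains material: 16 to 54% wrong choices against a patient marker with HR 12, and 73 to 96% in the HR 3 versus 1.5 contrast. Most of these figures assume forms missing at random; the tilt is smaller if nearly all converters have an informant.

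It would be too strong to say that AIC favours the informant model almost whatever the outcome data show. Against a very strong patient marker that is true only up to roughly 70 to 80% coverage. Nor does the point extend to the baseline CSF panel available for 200 patients: the Cox and AIC sentences list no biomarkers, which appear in that paragraph only in the logistic regression, where AIC is not named.

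**What to change.** Add to section 7, after the sentence on fit indices, wording such as:

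*Patient-rated and informant-rated models are compared by AIC and C-index only among patients who have both ratings at the predictor visit; every model in the comparison uses the same patients and the same events. The number of such patients and events is reported. The self-rating model in all completers is reported separately and is not part of the AIC comparison.*

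A short description of how completers without an informant rating differ from the rest would help readers judge how far the result generalises.

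The cost is one added passage and one data filter, with no new data. The downside is that patients without an informant rating leave this one comparison, so it rests on fewer events; they stay in the self-rating analysis of all completers.

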6.3. Recruitment

Participants of the already recruited ABC-PD cross-sectional cohort (ethic protocol: 284/2018BO1) will be asked to participate in the follow-up assessment. Patients who did not agree to participate in a longitudinal study or who have asked not to be contacted after the first cross-sectional assessment will not be contacted again. A drop-out rate of 20% is expected for follow-up retention. Therefore, investigation of 145 patients will be primarily conducted between January 2023 and June 2024. During the executive project phase, around 7 to 9 patients will be assessed per month. Patients will be contacted either via phone or in written form. Reasons for drop-outs will be registered for data analysis.

7. Statistics and Sample size estimation

All following hypotheses will be tested a priori; no post-hoc corrections of p-values will be conducted.

Characterization of study groups: Between-group comparisons at clinical visits will be conducted using Mann-Whitney-U or Welch test (two groups) or Jonckheere-Terpstra test (>2 groups) for numerical variables and χ^2 test or Exact Fisher Test for categorical variables. Post-hoc comparisons for IADL and cognitive variables between groups will be corrected for between-group covariates via linear regression models with group status as dummy coded variable. When follow-up cognitive groups are compared (PD-CN vs. PD-MCI vs. PDD), analyses with covariates will be run twice with reference category set as either PD-CN or PD-MCI.

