A structured and integrated exploration of biomaterial in combination with the analysis of the extensive quantitative dataset obtained in this study bears the chance for a better molecular, biochemical, and eventually functional understanding of one of the most debilitating symptoms associated with PD, i.e., cognitive deterioration.

For all patients, DNA, CSF, and plasma were sampled at baseline. Available data will be included into data analysis. This includes genetic information received from DNA analysis by using the NeuroChip, especially information on genetic variants associated with dementia and PD, as well as CSF levels of Abeta1-42, phosphor- and total Tau determined within the frame of the ABC-PD study. In collaboration with the company ADX, represented by [name] and [name], the following baseline CSF biomarkers were provided for further analysis of 200 patients: Abeta1-42, Abeta1-40, Abeta1-38, phosphor Tau 181, NF heavy, neurogranin, BASE-1, and alpha-synuclein.

At time of follow-up, a maximum of 50 PD patients is expected to give a third CSF sampling. Levels of CSF biomarkers indicating cognitive worsening [8, 9, 34-37] will be measured using the solid phase enzyme essays from Fujirebio Germany GmbH: Abeta1-42, Abeta1-40, phosphor- and total Tau. In addition, blood (serum) neurofilament light chain will be analysed in cooperation with [name]. med. [name] of the Universitätsklinikum Dresden.

8.5.4. *Storage of biomaterial*

All samples will be stored at -80°C until use. To maximize confidentiality, all biomarker samples and information associated with the samples will be coded to prevent the exposure of the subjects' information and identity. This coding process allows location and destruction of a sample at the subject's request. In addition, sample information is stored in one secured

electronic database, while biomarker data is stored in an independently secured database on a different computer. No one except the investigators of the UKT will have access to the database to deduce the identity of the patient.

9. Risks and possible adverse reactions, end of the study

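### The adjusted logistic model for dementia conversion would be better fitted with Firth's penalised likelihood, because about 26–27 conversions (12–14 if only new ones count) must carry several predictors

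*Combined protocol and SAP*

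**What the plan says.** Section 7 uses two kinds of model for conversion to Parkinson's disease dementia (PDD).

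- **Cox models.** In patients with all visits, the predictive values of IADL ratings, IADL type, cognitive status and the combined marker "will be calculated using multivariate Cox Proportional-Hazard models". AIC and the C-index are the fit measures.
- **Logistic model.** This asks whether baseline cognitive IADL impairment (FAQ quotient above 1.008) "predicted risk of PDD conversion independent of other clinical variables (e.g., cognitive status), biomarker profile, and covariates". Neither the number nor the full list of predictors is given.

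No penalised or exact estimator is named for either model, and there is no rule for an estimate that is not finite. Fisher's exact test appears in Section 7 only for describing groups.

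On numbers, Section 6.1 says "In total 182 patients will be invited to participate in the second" follow-up, Section 6.3 says "A drop-out rate of 20% is expected for follow-up retention", and the sample size text in Section 7 says "Therefore, a maximum of additional 15 converters are expected". Section 8.5.3 adds that "the following baseline CSF biomarkers were provided for further analysis of 200 patients", out of a cohort of 268. Section 7 does not say whether each PDD model counts all conversions since baseline or only those after the first follow-up.

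**The concern.** Ordinary ML logistic regression is biased away from zero when there are few events per coefficient. With very few events it can also separate, meaning that an estimate becomes infinite. The adjusted effect of cognitive IADL impairment is central to Section 4.1 and Aim 1.1, and the plan adds biomarkers and covariates to that model. An inflated odds ratio would make the marker look stronger than it is. If a model failed to converge, the remedy would be chosen after the data had been seen.

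**Working it through.** **Inputs.** Section 3.2: 182 re-assessed, 164 analysed, 17 with dementia. Section 6.3: 20% drop-out, 145 patients to be examined. Section 8.5.3: extended baseline CSF panel in 200 of 268 patients.

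**The plan's own figure.** Conversion risk = 17/164 = 10.37%. Attendees = 182 × 0.80 = 145.6 (stated as 145). Then 145 × 0.1037 = 15.0, which matches the stated 15. The product 147 × 0.1037 = 15.2 (147 = 164 − 17, no drop-out) also matches. The plan does not say which route it took.

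**Conversions available to the models.** Patients free of PDD at first follow-up number between 164 − 17 = 147 and 182 − 17 = 165. Drop-out is assumed unrelated to dementia.

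- New conversions: 147 × 0.80 × 0.1037 = 12.2, to 165 × 0.80 × 0.1037 = 13.7.
- Earlier converters who return: 17 × 0.80 = 13.6.
- All conversions since baseline: 13.6 + 12.2 = 25.8, to 13.6 + 13.7 = 27.3.
- Upper bound, if all 17 return and the stated maximum of 15 occurs: 32.
- New conversions with the extended CSF panel: 200/268 = 74.6%, so 0.746 × 12.2 = 9.1, to 0.746 × 13.7 = 10.2 (availability assumed unrelated to attendance and conversion). Baseline Abeta1-42 and tau come from the parent study, so only models using the extended panel are limited in this way.

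With six coefficients (assumed), this is 25.8/6 = 4.3 to 27.3/6 = 4.5 events per coefficient for all conversions, and 12.2/6 = 2.0 to 13.7/6 = 2.3 for new ones.

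**Simulation of ML against Firth.** There were 1,500 runs per setting. Cognitive IADL impairment had prevalence 37/164 and a true log odds ratio of 1.4. PD-MCI was present in 21/37 with it and 45/127 without it (the 45 is assumed). Three normal covariates and one binary covariate were added. The other log odds ratios were 1.0, 0.4, 0.3, 0.2 and 0.4 (assumed). Separated data sets were removed from the ML results only, which favours ML.

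| Events | ML mean | Firth mean | RMSE, ML | RMSE, Firth | Separation |
|---|---|---|---|---|---|
| 26 / 27 | 1.52 / 1.51 | 1.39–1.41 | 0.61 / 0.57 | 0.53 / 0.51 | none seen |
| 12 / 14 | 1.57 / 1.54 | 1.39–1.41 | 0.89 / 0.83 | 0.73 / 0.68 | 1–2% |
| 9 / 10 | 1.65 / 1.62 | 1.39–1.41 | – | – | 5–8% |

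A repeat simulation gave 1.60 (ML) against 1.42 (Firth) at 12 events, and 1.51 against 1.40 at 26. On the odds ratio scale, a bias of 0.1 is a factor of exp(0.1) = 1.11, and 0.15–0.2 is a factor of 1.16–1.22.

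**Smaller models.** With two to four predictors and 26–27 events, ML is biased by about 0.02–0.08 and no data set separated.

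**Cox model.** In a parallel simulation of 600 runs, ML and Firth means were 1.46 / 1.48 and 1.44 / 1.47 at 26 / 27 events, and 1.58 / 1.55 and 1.51 / 1.51 at 12 / 14. Separation was 2.2–2.7% at 12–14 events.

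**The case against.** The best defence is that the logistic model tests a baseline marker in a cohort that was free of dementia at baseline. All conversions since baseline are then the natural event set. At 26–27 events the bias of about 0.1 is small beside an RMSE near 0.6, and the ML Wald intervals had near-nominal coverage in the simulation (94.5–96.7%). The predictor count is assumed, and a short predictor list would remove most of the problem. All of this stands, and it limits the point to an improvement. It does not remove it: the plan expressly adds biomarkers and covariates, leaves the event set open, and Firth had the lower RMSE at both 26–27 and 12–14 events.

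A reader might infer more than the documents support:

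- **That the expected 15 is wrong.** It is given as a maximum and can be reproduced. Reaching it needs a risk of 15/132 = 11.4% to 15/117.6 = 12.8%, which the plan's argument of rising risk in later disease could supply.
- **That separation is likely.** Section 7 reports conversion "with higher rates of converters in patients with baseline status of cognitive ADL impairment (29.7"%), which is 11 of 37. Section 3.2 puts 10 of these in patients who also had PD-MCI, leaving 1 converter among 37 − 21 = 16 without PD-MCI. That cell would be empty in 44–49% of data sets, but only if new conversions alone count; separation also needs the combined marker entered beside both single markers, a coding the plan does not state. Even then the contrast within PD-MCI, which Section 4.1 is about, stays finite.
- **That third CSF samples starve a prediction model.** Section 8.5.3 says "At time of follow-up, a maximum of 50 PD patients is expected to give a third CSF sampling". These are taken at the outcome visit and cannot predict that outcome.
- **That the 94% and 92% power figures are offered for PDD.** Section 7 ties them to the FAQ interactions.
- **That the Cox models need the same change.** The bias gain there is small.

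**Conclusion.** The point holds as a low-cost improvement to the logistic PDD models. For the baseline marker with all conversions counted and about six predictors, ML overstates the log odds ratio by about 0.1. If only new conversions count, the excess is 0.15–0.2 with occasional separation, and it is larger in new-conversion models that use the extended CSF panel. Firth removes nearly all of the bias and lowers RMSE. With few predictors and all conversions counted, the gain is slight.

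The sizes rest on the assumed predictor count and effect sizes, an unchanged 10.4% risk, and 20% drop-out unrelated to dementia. The marker prevalence is the 37 patients above the cut-off of 1; Section 3.2 counts 35 above 1.008. Greater loss of patients with dementia would lower the event totals. The upper bound of 32 events would give 32/6 = 5.3 per coefficient, which is still few.

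**What to change.** In Section 7:

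1. Fit the multi-predictor logistic models for PDD with Firth penalised likelihood and report profile-likelihood intervals.
2. State for each PDD model whether it counts all conversions since baseline or new conversions only.
3. Keep ordinary Cox regression as planned, and name Firth Cox regression as the fallback if an estimate is not finite.

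The cost is a few sentences and a standard software option, with no added patients, visits or data. The downsides are that penalised estimates are slightly harder to compare with the earlier unpenalised results, and that AIC may be compared only between fits of the same kind.
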